5.4 Safety Analysis Sets

The Safety Analysis Set (SAF) consists of all randomized subjects who received at least 1 dose of study drug injection. Subjects will be included in the treatment group that the subject received as first injection.

There will be 2 additional safety analysis sets. The Modified Safety Analysis Set (mSAF) will consist of all subjects in the SAF excluding the 68 subjects who were included in the first futility analysis. Another additional safety set will consist of the 68 excluded subjects and will be notated as xSAF.

5.5 Pharmacokinetics Analysis Set (PKAS)

Pharmacokinetics are not applicable to this study.

5.6 Pharmacodynamic Analysis Set (PDAS)

Pharmacodynamics are not applicable to this study.

5.7 Immunogenicity Analysis Set

The Immunogenicity Analysis Set (IAS) will include subjects who received at least 1 dose of randomized study drug and for whom at least 1 post-transplant immunogenicity measurement is available.

The IAS will be used for analyses of the immunogenicity data.

6 ANALYSIS VARIABLES

6.1 Efficacy Endpoints

6.1.1 Primary Efficacy Endpoint

The primary efficacy endpoint is the proportion of patients with composite of all-cause mortality and adjudicated CMV EOD through 1 year post-transplant.

6.1.2 Secondary Efficacy Endpoints

6.1.2.1 Key Secondary Efficacy Endpoints

The 2 key secondary efficacy endpoints are:

- Time to first protocol-defined CMV viremia through 1 year post-transplant. CMV viremia is defined in the study protocol as CMV plasma viral ≥ 1000 IU/mL as assessed by the central laboratory.
- Time to first use of adjudicated CMV-specific AVT after study drug first injection through 1 year post-transplant.

6.1.2.2 Other Secondary Efficacy Endpoints

Additional secondary efficacy endpoints are:

- Proportion of patients with a composite endpoint of CMV viremia and CMV-specific AVT use per the adjudication committee
- Time to first event of either use of CMV-specific AVT or diagnosis of CMV EOD after study drug first injection through one year post-transplant. This endpoint is a composite endpoint based on the independent adjudication committee assessments of CMV-specific AVT and CMV EOD.
- All-cause mortality at 1 year post-transplant

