
Primary Variables
	
The primary endpoint of the study is the composite of overall mortality and CMV EOD through one year post-transplant.

Secondary Variables
	
Key secondary endpoints:
 
 
● Time to first protocol-defined CMV viremia [CMV plasma viral load <math>\geq 1000</math> IU/mL as assessed by the central laboratory] through 1 year post-transplant.
 
● Time to first adjudicated CMV-specific AVT through 1 year post-transplant.
 
 
Additional secondary endpoint:
 
 
● Time to first CMV-specific AVT for protocol-defined CMV viremia [CMV plasma viral load <math>\geq 1000</math> IU/mL as assessed by the central laboratory] or CMV EOD through one year post-transplant.
 

Exploratory Variables
	
 
● Clinical outcomes:       
 
➢ Overall mortality
 
➢ Incidence of CMV EOD
 
➢ Incidence of grade 3-4 aGVHD
 
➢ Incidence of severe cGVHD
 
➢ Incidence of grade 3 treatment-emergent infections other than CMV
 
➢ Maximum grade of aGVHD
 
➢ Maximum cGVHD score
 
➢ Relapse mortality (death due to relapse of the subject's primary disease)
 
➢ Non-relapse mortality (death due to causes unrelated to the subject's primary disease)
 
➢ Incidence of graft rejection
 
➢ Incidence of failure to engraft
 
➢ Time to engraftment
 
➢ Time to platelet recovery
 
➢ Incidence of relapse of primary disease requiring therapy
 
➢ Number of episodes of protocol-defined CMV viremia [CMV plasma viral load <math>\geq 1000</math> IU/mL as assessed by the central laboratory]
 
 
 

[figure not shown]
	
 
➤ Time to grade 3 treatment-emergent viral, bacterial, or fungal infections other than CMV
 
• Duration of hospitalization(s)
 
• Health economic/resource utilization
 
• Subjects' quality of life (EQ-5D, FACT-BMT, and Work Productivity and Activity Impairment Questionnaire: General Health [WPAI: GH])
 
• Immunogenicity Variables           
 
➤ T-cell responses to pp65
 
➤ gB-specific antibody levels
 
 
 

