	
The endpoint of time to first CMV-specific AVT for protocol-defined CMV viremia or CMV EOD through 1 year post-transplant will be analyzed using a Cox proportional hazards model as described above.
 
Incidence of overall mortality, CMV EOD, grade 3-4 aGVHD, severe cGVHD, grade 3 infections other than CMV, relapse mortality, non-relapse mortality, graft rejection, failure to engraft, and relapse of primary disease requiring therapy will each be tested using a stratified analysis of the binary response using a CMH test to account for the stratification variables used as part of the randomization.
 
Number of episodes of protocol-defined CMV viremia will be compared between treatments using a stratum-adjusted Kruskal-Wallis test, adjusting for donor-recipient relatedness and donor CMV status.

	
To estimate the association between CMV viremia and mortality, a multivariable Cox proportional hazards model will be constructed in a time-dependent manner. The model will be adjusted for the factors used to stratify the randomization. CMV viremia will be treated as a time-dependent variable, starting at the time of the first occurrence of protocol-defined CMV viremia.
 
The maximum grade of aGVHD, maximum cGVHD global score, and duration of hospitalizations will each be tested using a stratum-adjusted Kruskal-Wallis test.
 
The treatment effect on time to engraftment and time to platelet recovery will each be analyzed in a Cox proportional hazards model including the factors used to stratify the randomization.
 
Treatments will be compared with respect to each domain of the EQ-5D, the FACT-BMT, and productivity outcomes from the WPAI:GH using analysis of covariance (ANCOVA) of change from baseline to final visit with treatment, donor-recipient relatedness, and donor CMV serostatus as factors and baseline value as covariate.

Safety Analysis
	
The SAF will consist of all randomized subjects who have received at least 1 study drug injection. This analysis set will be used for all summaries of AEs, reactogenicity, clinical lab data, physical exams, vital signs and subject survival through 1 year post first study drug injection. All recorded AEs will be listed, including duration, outcome, toxicity grade, and association with use of study drug.

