### 2.3.2 Secondary Variables

The 2 key secondary endpoints are:

- Time to first protocol-defined CMV viremia [CMV plasma viral  $\geq 1000$  IU/mL as assessed by the central laboratory] through 1 year post-transplant.
- Time to first adjudicated CMV-specific AVT through 1 year post-transplant.

Additional secondary endpoints are:

- Time to first CMV-specific AVT for protocol-defined CMV viremia [CMV plasma viral load  $\geq 1000$  IU/mL as assessed by the central laboratory] or CMV EOD through one year post-transplant.

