### **7.4.2 Analysis of Secondary Variables**

#### **7.4.2.1 Key Secondary Variables**

A Cox proportional hazards model will be used to assess the effect on the time-to-first protocol-defined CMV viremia through 1 year post-transplant. Protocol-defined CMV viremia is defined as a CMV plasma load  $\geq 1000$  IU/mL as assessed by the central laboratory.

The Cox model will contain the same terms as the 1 described above. Vaccine efficacy will be estimated as:

$$VE = 1 - \text{hazard ratio, and 95 \% CI will be provided.}$$

To compare the treatment effect on protocol-defined CMV viremia between ASP0113 and placebo, the following null hypothesis will be constructed:

$$H_0: VE \leq 20\%.$$

The accompanying alternative hypothesis is:

$$H_1: VE > 20\%.$$

The P value for the above hypothesis tests will use a Wald statistic using the Cox model parameter estimate for the treatment effect,  $\theta_t$ :

$$Z = (\theta_t - \ln(1-20\%))/S.E.(\theta_t)$$

The 95% CI for VE will be calculated by taking 1 minus the 95% CI for the hazard ratio. Alternative hypothesis will be accepted if the 95% CI for VE excludes 20%.

The hazard rate of first adjudicated CMV-specific AVT through 1 year post-transplant and for first CMV-specific AVT for protocol defined viremia will be analyzed similar to the analysis for CMV viremia. These analyses will test for simple superiority (0% efficacy margin) rather than use a 20% efficacy margin.

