#### **7.4.2.2 Other Secondary Variable**

The endpoint of time to first CMV-specific AVT for protocol-defined CMV viremia or CMV EOD through 1 year post-transplant will be analyzed using a Cox proportional hazards model which includes effects for treatment, donor CMV serostatus, and donor-recipient relatedness.

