7.4.2.3.2 Time to CMV-specific Antiviral Therapy or End Organ Disease

A composite endpoint of time to first event between CMV-specific Antiviral Therapy (AVT) use and CMV End Organ Disease (EOD) through 1 year post-transplant (i.e., through day 380 from transplantation) will be analyzed for FAS and mFAS. Both CMV-specific AVT use

and CMV EOD will be based on the assessment of the adjudication committee. A subject without any event will be censored on the last study evaluation according to the end of study eCRF. A subject who dies prior to reporting CMV-specific AVT or EOD will be handled using a competing risks model.

This endpoint will be analyzed using the Cox proportional subdistributional hazards model and CIFs (to account for the competing risk of death) and CMH method, as described above for the key secondary endpoints.

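### The SAP replaces the protocol's additional secondary AVT endpoint with one that states no central-laboratory viremia condition, gives no reason in the supplied documents, and leaves no time-to-event analysis of AVT explicitly tied to central-laboratory viremia

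*SAP*

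**What the plan says.** **Protocol.** Section 2.3.2 lists as an additional secondary endpoint "Time to first CMV-specific AVT for protocol-defined CMV viremia", with viremia specified as a central-laboratory load of at least 1000 IU/mL, or CMV EOD, through one year. The Synopsis repeats it. Section 7.4.2.2 gives the analysis: "The endpoint of time to first CMV-specific AVT for protocol-defined CMV viremia or CMV EOD through 1 year post-transplant will be analyzed" with a Cox model containing treatment and the two stratification factors. Section 7.4.2.1 adds that "first CMV-specific AVT for protocol defined viremia will be analyzed similar to the analysis for CMV viremia", tested for simple superiority instead of against the 20% margin.

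**SAP.** Section 6.1.2.2 gives the endpoint as "Time to first event of either use of CMV-specific AVT or diagnosis of CMV EOD after study drug first injection through one year post-transplant" and adds: "This endpoint is a composite endpoint based on the independent adjudication committee assessments of CMV-specific AVT and CMV EOD". Section 7.4.2.3.2 analyses "A composite endpoint of time to first event between CMV-specific Antiviral Therapy (AVT) use and CMV End Organ Disease (EOD) through 1 year post-transplant", again on the committee's assessments, by a subdistribution hazards model, cumulative incidence functions and CMH. Neither section mentions a viral load.

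**Change log.** SAP 8.1 lists changes from Version 2 to Version 3.0. It records and explains a newly added viremia and AVT composite, but it does not mention the redefinition of the AVT/EOD endpoint.

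**The concern.** The SAP's introduction presents it as a more detailed elaboration of the protocol's analysis. Removing a stated condition from an event definition goes beyond elaboration. The SAP commits the study report to documenting changes from the final SAP, and its log covers changes between two SAP versions. A change from protocol to SAP that predates Version 2 falls outside both, so a reader of the results could not tell why the reported endpoint differs from the protocol's.

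The condition has a purpose. The Synopsis and Protocol 2.2.1 allow pre-emptive therapy to be started on local or central results together with clinical condition. Protocol 1.5 and 2.2.1 warn that vaccine plasmid can produce false-positive results in some PCR assays, and 1.5 adds that this can lead to unnecessary AVT. Requiring central-laboratory viremia guards directly against counting such starts. Under the SAP wording, that protection depends on what the committee does.

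**Working it through.** No figure in the plan needs reproducing. The check compares the definitions and asks whether another analysis fills the gap.

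**1. How the same history is classified**

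| History within one year | Protocol wording | SAP wording |
|---|---|---|
| AVT for central viremia of at least 1000 IU/mL | Event | Event if the committee accepts the AVT |
| AVT on a local result or clinical condition; no central value of at least 1000 IU/mL; no EOD | Not an event | Event if the committee accepts the AVT |
| EOD diagnosed, no AVT | Event only if EOD counts in itself | Event if EOD is adjudicated |
| EOD, then AVT for it | Event at AVT start or at EOD diagnosis, depending on the reading | Event at the first of the two that is adjudicated |

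The first row can differ if the committee rejects a start that meets the viral-load condition, and the second can differ the other way. The last two depend on an ambiguity in the protocol: EOD may be an event in itself or only a second indication for AVT. The SAP settles this silently, in favour of an event in itself.

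**2. Whether another SAP analysis fills the gap**

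- SAP 7.4.2.1: time to central-laboratory viremia, without AVT.
- SAP 7.4.2.2: time to adjudicated AVT, with no viremia condition stated.
- SAP 7.4.2.3.1: viremia *and* AVT, but as a proportion tested by CMH. The text does not say whether *and* means both or either.
- SAP 7.4.2.3.2: time to adjudicated AVT or EOD, with no viremia condition stated.

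None is a time-to-event analysis of AVT explicitly tied to central-laboratory viremia.

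**3. Whether AVT starts and central viremia are interchangeable (phase 2, Protocol 1.3.2.2)**

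The protocol reports AVT in 47% (ASP0113) against 61.8% (placebo), and central viremia in 33% against 62%. The AVT analysis set excluded 2 subjects with false-positive local results. Table 3 gives 40 and 34 subjects.

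- Placebo AVT: with 32 to 34 subjects, only 21/34 = 61.8% fits. The 2 exclusions are therefore in the ASP0113 arm, leaving 38.
- ASP0113 AVT: 18/38 = 47.4%.
- ASP0113 central viremia: 13/40 = 32.5% or 13/39 = 33.3%, so 13 either way.
- Placebo central viremia: 21/34 = 61.8%.
- Minimum AVT starts without central viremia at any time: ASP0113 18 − 13 = 5; placebo 21 − 21 = 0.

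These are lower bounds, and the true number in either arm could be higher. They assume that both rates describe the same per-protocol subjects. The viremia threshold was 500 copies/mL on a different assay, and no conversion to IU/mL is given. The result shows only that AVT starts and central-laboratory viremia are not the same thing.

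**The case against.** The strongest reply is that adjudication may be how the SAP puts the protocol wording into operation. Deciding that AVT was given *for* viremia or EOD requires someone to attribute an indication, and Protocol 10.2 gives adjudication of AVT initiation to the committee. If the charter requires central-laboratory viremia, and EOD counts in itself, the two endpoints could coincide. This stands as a possibility. However, neither document says that adjudicated AVT requires 1000 IU/mL, and the charter is not supplied.

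The safeguards are also substantial. Protocol 2.2.1 requires Sponsor-approved local laboratories and a paired central sample with every local one. Sites with an unacceptable PCR assay need another accepted assay or method. For pp65 antigenemia, discordant local and central results must be reported to the Medical Monitor, and both tests are repeated if such a subject is treated. SAP 7.4.2.2 describes the committee as independent and blinded. These measures reduce the risk but do not restore the missing definition.

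The change log starts at Version 2, so an earlier version may have given a reason. The finding is therefore limited to the supplied documents.

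A reader might infer from phase 2 a minimum share of AVT starts that the two definitions would classify differently in this trial. The documents do not support that. The phase 2 account describes no adjudication, the assay and threshold differed, and some of the 5 starts may have been for EOD. The 2 known false-positive starts had already been removed, so the remaining discordance is not evidence for the false-positive mechanism.

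**Conclusion.** The definitions differ on their face. The supplied documents give no reason, and the SAP as written leaves the protocol's additional secondary endpoint without an explicit analysis. This should be corrected, but the consequence is confined to a non-key secondary endpoint. The primary and key secondary definitions are unaffected.

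No size can be given. How far the endpoints diverge depends on the unseen charter and on how often AVT is started without central viremia, so the difference may be zero.

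Two stronger readings are not supported:

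- A reader might infer that the change biases the result in a known direction, because the foreseen false positives concern ASP0113 recipients. The documents do not show how many such starts would survive the safeguards and adjudication, and committee decisions could also move classifications the other way.
- A reader might extend the criticism to the key secondary AVT endpoint. The protocol itself defines that endpoint as adjudicated AVT without a viral-load condition, so the SAP has not changed its event definition in this respect.

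**What to change.** In SAP 6.1.2.2 and 7.4.2.3.2, add the protocol-worded endpoint (AVT with central-laboratory viremia of at least 1000 IU/mL, or CMV EOD) as a time-to-event analysis alongside the adjudicated AVT-or-EOD endpoint. Neither need be ranked as supportive.

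Before unblinding, settle three points the protocol leaves open:

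- the window linking the central value to AVT initiation, since without one a long-resolved viremia could qualify a later, unrelated start;
- the rule when the central sample is missing;
- whether EOD is an event in itself or only an indication for AVT.

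State in the SAP that the adjudicated endpoint departs from the protocol, and why. If the adjudication charter already requires central-laboratory viremia of at least 1000 IU/mL for adjudicated AVT, state that instead.

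The cost is one derivation, one model and a short documented reason. Protocol 5.3.1 and Table 1 footnote 16 already require a central sample at AVT initiation, so no new data collection is needed.

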6.1.3 Exploratory Efficacy Endpoints

Exploratory efficacy endpoints include the following efficacy outcomes.

- Clinical outcomes:
 - Composite endpoint of all-cause mortality and adjudicated CMV EOD at 6 months post-transplant
 - All-cause mortality at 6 months post-transplant

- Incidence of adjudicated CMV EOD
- Incidence of investigator-reported CMV EOD
- Incidence of grade 3-4 aGVHD
- Incidence of grade 3 treatment emergent viral, bacterial, or fungal infections other than CMV
- Maximum grade of aGVHD
- Relapse mortality (death due to relapse of the subject's primary disease)
- Non-relapse mortality (death due to causes unrelated to the subject's primary disease)
- Incidence of engraftment (Yes/No)
- Incidence of graft rejection/poor graft function
- Incidence of relapse of primary disease requiring therapy
- Number of episodes of protocol-defined CMV viremia [CMV plasma viral load ≥ 1000 IU/mL by the Abbott RealTime CMV assay as assessed by the central laboratory]
- Association between CMV viremia and mortality
- Duration of hospitalization(s), in days:
 - Total duration of ICU stays
 - Total duration of stays in step down units
 - Total duration of stays in hospital general medical/surgical ward
 - Total duration of all hospitalizations
- Total number of days in emergency room and total number of visits to emergency room

Death will be classified as relapse mortality (adjudication CRF indicates 'Death due to relapse of persistent disease') or non-relapse mortality ('Death not due to relapse of persistent disease') by a blinded adjudication committee. If a death has not been adjudicated (e.g., discovered through public records search without a corresponding adverse event) then it will not be considered in either the relapse or the non-relapse mortality analyses.

In determining the number of episodes of protocol-defined CMV viremia, an episode will be considered to start when a viral load is load ≥ 1000 IU/mL and previous viral loads are < 1000 IU/mL. An episode will be considered to end when 2 consecutive viral loads < 1000 IU/mL separated by at least 1 week are observed.

Treatment emergent infections are those occurring after the first dose of study drug and up to 1 year post-transplant.

Total duration of hospitalization will be the sum of hospitalization days added up over all the hospitalizations experienced by a subject within 1 year after transplantation, and will include days in intensive care, step down units and general medical/surgical wards. For comparing treatments, total duration of hospitalization will be normalized to days of hospitalization per year by dividing number of hospitalization days by the number of days of follow-up (starting from day of transplantation), times 365. For example, if a subject has a 3-day hospitalization and a 5-day hospitalization, and is lost to follow-up at 64 days post-transplant, then the value of 45.625 days/year will be used for this subject ($365 \times 8 / 64 = 45.625$).

The same method of normalization will be used for total duration of stays in ICUs, total duration of stays in step down units, total duration of stays in hospital general medical/surgical ward, and total number of emergency room days. The number of emergency room visits will not be normalized.

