**Note:** CMV plasma viral loads may be performed at a local laboratory approved by the Sponsor and at the discretion of the Investigator. However, every time a viral load sample is sent to the local laboratory a sample will also be sent to the central laboratory for

confirmatory testing. Pre-emptive therapy may be started based on the central or local laboratory assessment and the subject's clinical condition.

As 1 of the plasmids of the ASP0113 vaccine codes for the pp65 antigen, the theoretical possibility of interference with the pp65 antigenemia assay has been raised. At present, there are no data to suggest that such interference occurs. However, to ensure patient safety and study integrity, sites that use pp65 antigen as their local methodology for the detection of CMV infection must adhere to the procedures defined below as a condition of participation in the trial.

- The local pp65 antigenemia results must be entered into the eCRF database within 72 hours (or next business day) of receipt to facilitate in-time monitoring of results.
- The Medical Monitor must be called within 48 hours (or next business day) if the pp65 antigenemia test is positive and the central laboratory PCR viral load result is negative.
- Both the pp65 antigenemia and the central laboratory test must be repeated within 48 hours if the local pp65 antigenemia result is positive, the central laboratory PCR viral load result is negative and the subject is treated with CMV-specific AVT.

The plasmids in the study vaccine may interfere with certain PCR assays. If a PCR assay is used that amplifies the genes UL55/gB or UL83/pp65, this could result in either a false positive viral load or unblinding of the study subject.

Sites that are determined to have unacceptable PCR assay in their local laboratory but were able to determine a Sponsor deemed acceptable work practice flow for utilizing another acceptable local assay or methodology will be allowed to participate in the trial.

**Note:** Local CMV plasma viral load testing may be performed only at a local laboratory approved by the Sponsor.

Adjudicated CMV-specific AVT will be assessed for subjects up to 1 year following transplant through the primary study period (through day 365/V14).

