## 5.3 Efficacy and Immunogenicity Assessments

### 5.3.1 CMV Plasma Viral Load Assessment

CMV plasma viral load will be assessed by Abbott's RealTime CMV assay using a fully automated system entailing extraction of CMV DNA and amplification of viral DNA with virus specific primers and probes.

A subject's viremia status will be monitored by the site on a regular schedule, as outlined in [Table 1a](#), and at any time it is clinically indicated. Central laboratory measurements for routine surveillance of viremia will be performed at the following time points:

- Every 7 days (weekly  $\pm$  2 days) from days 0 to 100.
- Every 14 days (every other week  $\pm$  5 days) from days 101 to 180,
- Every 30 days (every 30 days  $\pm$  5 days) from days 181 to 365.

A central laboratory measurement will also be performed at the initiation of CMV-specific AVT, when clinically indicated and/or each time a local laboratory is used to assess the viral load. Upon initiation of CMV-specific AVT, plasma viral load testing will be performed at least weekly until the CMV-specific AVT is discontinued, at which point, the regularly scheduled plasma viral load assessments will resume. Please refer to the Laboratory Manual for more exact instructions.

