16. Plasma viral load by the central laboratory will be monitored weekly (± 2 days) during days 0-100, every other week (± 5 days) during days 101-180, every 30 days (± 5 days) during days 181-365, at the initiation of CMV-specific AVT, when clinically indicated, and every time a viral load sample is sent to the local laboratory. When CMV-specific AVT is initiated, a central CMV viral load will be obtained a minimum of weekly until CMV-specific AVT is discontinued. Thereafter, the regularly scheduled viral load assessments will resume according to the scheduled protocol assessments.
17. The first dose is to be given at day -14 to -3 prior to transplant and within 72 hours prior to the start of chemotherapy and radiation therapy for conditioning.
18. The subject must be monitored directly for the first 15 minutes of the injection. The subject must be in the clinic, but does not require direct monitoring, from 15 minutes through 1 hour after the injection.
19. Local reactogenicity will be evaluated 1 hour (± 10 minutes) after each injection and for each of the 7 consecutive days following each injection beginning approximately 24 hours following each dose (day 1-7 postdose). The assessments for each of the 7 consecutive days following an injection will be done by the subject and reported to the site via diary. When reactogenicity is reported as an AE, it is to be followed until resolution or medically stable. All local reactions \geq grade 3 (Protocol Appendix 7) require confirmation by a health care professional.
20. The date of transplant (donor cell infusion) defines day 0 and all visit days are relative to day 0. Based on this schedule, V3 may occur prior to or after the day of transplant, day 0.

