7.4.3.1.2 Number of Episodes of Protocol-defined CMV Viremia

Number of episodes of protocol-defined CMV viremia [CMV plasma viral load ≥ 1000 IU/mL by the Abbott RealTime CMV assay as assessed by the central laboratory] will be compared between treatments using the stratum-adjusted Kruskal-Wallis test, adjusting for donor-recipient relatedness and donor CMV status.

Number of episodes of protocol-defined CMV viremia may be affected by duration of follow-up. Therefore, as a supporting analysis this variable will be compared between

treatments using a log-linear model with treatment, donor-recipient relatedness, and donor serostatus as factors and the log of time of follow-up as a covariate.

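### The SAP 6.1.3 rule that ends a CMV viremia episode does not fit the sampling schedule, so the exploratory episode count depends partly on how often a subject is tested

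*SAP*

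**What the plan says.** The number of protocol-defined viremia episodes is an exploratory endpoint. SAP 6.1.3 starts an episode at a central load of at least 1000 IU/mL when "previous viral loads are < 1000 IU/mL". On closing one, it says: "An episode will be considered to end when 2 consecutive viral loads < 1000 IU/mL separated by at least 1 week are observed". I found no other start or end rule in the protocol or SAP.

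Sampling is set in footnote 16 to SAP Table 1 (SAP section 2):
- Early phase: "Plasma viral load by the central laboratory will be monitored weekly (± 2 days) during days 0-100".
- Middle phase: "every other week (± 5 days) during days 101-180".
- Late phase: "every 30 days (± 5 days) during days 181-365".

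During CMV-specific antiviral therapy (AVT), Protocol 5.3.1 treats weekly as a floor: "plasma viral load testing will be performed at least weekly until the CMV-specific AVT is discontinued". The regular schedule then resumes. Central samples are also drawn when clinically indicated, and Protocol 2.2.1 adds that "every time a viral load sample is sent to the local laboratory a sample will also be sent to the central laboratory".

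Under SAP 7.4.3.1.2 the count "will be compared between treatments using the stratum-adjusted Kruskal-Wallis test". A supporting log-linear model carries the log of follow-up time as a covariate.

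**The concern.** The end rule asks for at least 7 days between two samples, while the schedule places samples nominally 7 days apart with a window on each. On the ordinary reading of consecutive as adjacent, two fully compliant clear samples may fail to close an episode because one was drawn a day late or the next a day early. Extra samples make closure harder: each splits a gap that might have qualified. If viremia returns before a qualifying pair has been seen, the second episode is absorbed into the first.

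The count then reflects testing frequency as well as the virus. Testing frequency is not random: it follows AVT, local testing and clinical suspicion. The log-linear model adjusts for length of follow-up, not for sampling density. Elsewhere the SAP allows for visit windows (SAP 7.4.2.1 extends the viremia window to day 380 for this reason); the episode rule does not.

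**Working it through.** The documents give no figure for gaps or episode counts, so there is none to reproduce. The distribution of draw days within the windows is not given either, so it is assumed and a range is shown.

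**1. Gap between adjacent weekly draws.** With offsets a and b from the nominal days, each from −2 to +2, the gap is 7 + b − a. It runs from 7 − 4 = 3 to 7 + 4 = 11 days and falls below 7 when b < a.
- Uniform, independent offsets: 10 of 25 pairs have b < a, so 40%.
- Weights 0.025, 0.125, 0.70, 0.125, 0.025: (1 − Σp²)/2 = (1 − 0.5225)/2 = 24%.
- Every gap exactly 7 days: 0%, since 7 days qualifies.

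**2. Does one missed pair hold the episode open?** With k clear weekly samples in a row, no adjacent pair qualifies only if the offsets fall strictly throughout. Under uniform offsets the probability is C(5,k)/5^k.

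| Clear samples k | Still open, adjacent reading | Still open, unbroken run spanning ≥ 7 days |
|---|---|---|
| 2 | 10/25 = 40% | 40% |
| 3 | 10/125 = 8% | 0% |
| 4 | 5/625 = 0.8% | 0% |
| 5 | 1/3125 = 0.03% | 0% |
| 6 | 0% | 0% |

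Three weekly draws span at least 14 − 4 = 10 days, so the run reading always closes by the third.

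**3. Later phases.** On days 101-180 the gap is 14 + b − a with offsets from −5 to +5. It is below 7 only when a − b ≥ 8, which is 3 + 2 + 1 = 6 of 121 pairs, or 5.0%. Two such shortfalls in succession are impossible, so the third clear sample always closes the episode. On days 181-365 the shortest gap is 30 − 10 = 20 days, so none fails.

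**4. Denser sampling.** At alternating 3- and 4-day gaps, no adjacent pair reaches 7 days while that pattern lasts. A run-based rule closes at the third sample, since 3 + 4 = 7.

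**5. Effect on a count.** Simulated subject with two 14-day episodes, mean episodes counted:

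| Clear days between | Weekly ±2 (uniform), adjacent rule | Twice weekly throughout, adjacent rule | Twice weekly throughout, 7-day run rule |
|---|---|---|---|
| 14 | 1.35 | 1.00 | 2.00 |
| 21 | 1.82 | 1.00 | 2.00 |
| 28 | 1.97 | 1.00 | 2.00 |
| 42 | 2.00 | 1.00 | 2.00 |

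On weekly sampling with 14 clear days, the 7-day run rule gives about 1.4, so there it changes little. Its value lies in the dense-sampling column, where two readings of one sentence differ twofold.

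**The case against.** The case against a serious fault is strong, and most of it stands.

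- **Delay, not failure.** On scheduled weekly draws a missed pair only postpones closure: 92% of episodes are closed by the third clear sample and over 99% by the fourth. After day 100 the scheduled gaps almost always qualify.
- **Dense sampling is neither scheduled nor permanent.** A reader might infer that an episode under AVT can never end. The documents do not support that. Weekly is the required minimum, a 7-day gap qualifies, and the regular schedule resumes after AVT. The twice-weekly column assumes a frequency that the documents do not schedule. If such sampling stops 7 days after clearance, the adjacent rule counts about 1.7, 1.95 and 2.0 at 21, 28 and 42 clear days.
- **Consecutive may mean an unbroken run.** On that reading the dense-sampling problem disappears. The SAP does not say which is meant, and that ambiguity is itself part of the point.
- **Asking for a week of clearance is legitimate.** Nothing in the documents makes a return after 14 clear days a true second episode. Most merging on weekly draws comes from requiring two clear samples at all: with an assumed geometric number of clear samples averaging 2 to 8, the 1-week gap adds about 5 to 11 percentage points (61% against 50%, down to 18% against 13%).
- **Bias toward no difference is not shown.** A reader might infer it because phase 2 AVT use was 47% on ASP0113 and 61.8% on placebo (Protocol 1.3.2.2). No arm comparison can be computed from the documents, and the rule cannot alter whether a subject has none or at least one episode.
- **The start rule.** Taken literally it bars any second episode, since an earlier load was at least 1000 IU/mL. An endpoint that counts episodes and has an end rule plainly means otherwise. This is a wording repair, not evidence that counts are capped at one.

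**Conclusion.** The point holds in a limited form. On the adjacent-sample reading, the 1-week minimum without tolerance does not fit a schedule whose compliant weekly gaps run from 3 to 11 days. The miss rate per adjacent pair lies between 0% and 40%, depending on an assumed draw-day distribution with independent offsets. While central sampling stays denser than weekly, the rule cannot be met. Merging needs viremia to return before a qualifying pair, so the risk is concentrated in quick recurrences before day 100 or under dense sampling. It is a possibility, not a certainty.

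Only one exploratory endpoint is touched. The primary composite, time to first viremia and AVT use do not rely on this rule. The size and direction of any effect on the arm comparison cannot be determined from the documents.

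**What to change.** In SAP 6.1.3, before unblinding:

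1. End an episode at an unbroken run of central viral loads below 1000 IU/mL whose first and last samples are at least 7 days apart, whatever samples lie between.
2. Start a new episode at the first load of 1000 IU/mL or more after the previous episode has ended.

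Extra clear samples then can no longer keep an episode open. Two clear weekly draws less than 7 days apart will still not close one (up to 40% of pairs), but the third always will.

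If a visit-window tolerance is wanted, it should be stated as a separate choice, with the count reported with and without it as a sensitivity analysis. Subtracting one ±2 day window to reach 5 days does not cover the schedule: both visits have windows, the shortest compliant gap is 3 days, and 3 of 25 pairs (12%) still fail a 5-day threshold under uniform offsets.

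Cost: two sentences and one derivation program, with no new data. Some episodes will end earlier than under the adjacent-sample rule.
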